### 7.3.2 Secondary analyses

In addition to the primary analysis (time to first event), crude rates will be displayed for the primary and key secondary endpoints. The interpretation of crude rates has to take into account that the likelihood to observe an event increases with a longer survival and/or observation period; therefore a difference between the treatment groups with regard to the actual observation period will be explored.

The key secondary endpoints are ~~is~~ time to the first occurrence of **any of the following by adjudication confirmed components:**

- ~~CV death (including fatal stroke, fatal MI and sudden death), non-fatal MI (excluding silent MI), non-fatal stroke (3-point MACE)~~
- Composite renal endpoint (renal death, sustained ESRD, sustained decrease of ~~50~~ **40%** or more in eGFR)

After non-inferiority has been established for the primary endpoint (~~4~~ **3**-point MACE), the same endpoint and the composite renal endpoint (~~at the final analysis~~) will be tested for superiority. ~~In case of significant superiority of the 4-point MACE and/or the composite renal endpoint, the 3-point MACE will then be tested for superiority.~~

For the primary, ~~and~~ key secondary endpoints ~~and~~, their individual components; **and** the time-to-event analyses will be based on the randomization date; for the other endpoints **time-to-AE analyses** the date of first study drug intake will be used.

Proprietary confidential information.

© 2016 Boehringer Ingelheim International GmbH or one or more of its affiliated companies. All rights reserved.

This document may not - in full or in part - be passed on, reproduced, published or otherwise used without prior written permission.

Other endpoints:

**Proprietary confidential information.**

**© 2016 Boehringer Ingelheim International GmbH or one or more of its affiliated companies. All rights reserved.**

This document may not - in full or in part - be passed on, reproduced, published or otherwise used without prior written permission.

The key secondary endpoints and the individual components of the primary and key secondary endpoints will be analysed as time to first occurrence. In addition, crude rates will be displayed. Chi-Square tests will be applied for efficacy data; these tests will be interpreted in an exploratory sense, two-sided p-values without alpha-adjustment will be presented. Wilson confidence intervals will be reported for the proportion of patients with primary and key secondary endpoints; ~~in addition logistic regression models will be applied.~~

### 7.3.3 Safety analyses

All safety data will be displayed and analysed (Treated Set, 'as randomized') using descriptive statistical methods. No formal inferential analysis is planned for safety comparisons. AEs will be coded using the medical dictionary for drug regulatory activities (MedDRA) coding dictionary. All events with an onset after the first dose of study medication up to a period of seven days after the last dose of study medication will be assigned to the treatment phase for evaluation; in addition, all AEs after the first dose of study medication will be displayed by randomized treatment group. Laboratory values taken after the first dose of randomized treatment up to a period of seven days after the last intake of treatment will be assigned to the treatment phase for evaluation. Laboratory values will be compared to their reference ranges and frequency tables will be provided for the number of patients within and outside the reference range. Changes from baseline in blood pressure and pulse rate will be summarised by treatment group. For hypoglycaemic events the incidences and the treatment-time adjusted frequencies will be displayed.

### 7.3.4 Interim analyses

An independent Data Monitoring Committee (DMC) will review safety and efficacy data and make recommendations whether to continue or terminate the study. As described in [Section 3.1.1](#) the DMC analyses and operations will be formally separated from the sponsor, the investigators and the Steering Committee. The details on its procedures and interactions are provided in a separate DMC Charter.

~~It is planned that there will be one formal interim analysis for CV efficacy after 70% of the expected primary CV events, i.e. after 437 patients have experienced an adjudicated primary CV endpoint. The interim analysis will be performed at the one-sided alpha level of 1.0%;~~

Proprietary confidential information.

© 2016 Boehringer Ingelheim International GmbH or one or more of its affiliated companies. All rights reserved.

This document may not - in full or in part - be passed on, reproduced, published or otherwise used without prior written permission.

~~according to Haybittle-Peto (East version 5.4), this results in a one-sided alpha of 2.12% for the final analysis. The first test will be on non-inferiority of the primary endpoint, in case of significance followed by the superiority tests for the composite CV endpoints outlined in Section 7.2. No confirmatory interim analysis will be performed for the composite renal endpoint, i.e. for the renal endpoint superiority will formally be tested only once after regular or premature study termination, respectively. In case non-inferiority has not yet been demonstrated, the study will be continued as planned unless the interim results indicate major safety concerns. In case of demonstrated superiority of the primary variable at the interim analysis, the DMC may recommend stopping the study; non-inferiority of the primary endpoint may lead to early study termination if the DMC considers it unrealistic to achieve superiority. Further details will be given in the DMC Charter.~~

Prior to the **interim final** analysis, the SC will evaluate available external data with relevance for the superiority test strategy and consequently may suggest to the sponsor adapting the assumptions and study size, respectively.

~~In addition~~ there will be interim analyses for safety, based on all adverse events as recorded, but these interim analyses may not lead to early study termination due to demonstrate non-inferiority or superiority; therefore these interim safety analyses have no negative impact on the alpha-level.

### 7.3.5 Pharmacokinetic analyses

Not specified in this protocol

### 7.3.6 Pharmacodynamic analyses

Not specified in this protocol

### 7.3.7 Pharmacogenomic analyses

No prespecified pharmacogenomic analyses planned.

## 7.4 HANDLING OF MISSING DATA

Patients with temporary or permanent study treatment termination will be followed up for CV events. Details on how to handle missing data will be outlined in detail in the trial statistical analysis plan (TSAP).

### CV safety and other safety endpoints (including renal safety endpoints)

It is not planned to impute missing values.

### Diabetes related endpoints

Missing efficacy data for continuous variables for patients who discontinue the study treatment prematurely or miss a visit will be estimated by their last observed data. Missing

Proprietary confidential information.

© 2016 Boehringer Ingelheim International GmbH or one or more of its affiliated companies. All rights reserved.

This document may not - in full or in part - be passed on, reproduced, published or otherwise used without prior written permission.

data for binary efficacy endpoints for patients who discontinue the study treatment prematurely will be considered as non-responders (worst case-scenario).

Methods to handle any other exceptional cases will be considered before unblinding the data and will be applied in a manner consistent with other trials of this type. The evaluability of patients with deviations from the protocol likely to confound the primary endpoint will be decided prior to unblinding.

The impact of all methods of handling missing data will be analysed using a sensitivity analysis by performing an analysis of the original data (i.e. without any imputation).

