C The study is event driven. The number of confirmed adjudicated primary endpoint events will be continuously monitored during the trial. Based on the available number of events the projected number of expected future events will be calculated. As soon as the projection reliably suggests that the total number of patients with a by adjudication confirmed primary endpoint event will reach 625 **611 within the next 24 weeks**, the trial team will perform respective actions to stop the trial. From this time point on, all patients are expected to perform their last visit (EOT visit) within the **regular proposed** time schedule, **which means within the next 24 weeks communicated via an investigator letter**. A follow-up visit will take place **one week 30 days** after the end of treatment (EOT visit).

Patients who discontinue study drug prematurely should continue study visits until study end. Study assessments may be omitted if a patient is willing to return to the pre-defined study visits, with exception **collection of adverse events, outcome events, concomitant therapy and laboratory testing of creatinine for the calculation of the eGFR**.

If a patient who prematurely discontinued study drug is not willing to return to the pre-defined study visits, at minimum a yearly telephone call (preferably every 6 months) and a telephone call at study end will be required, to document the occurrence of outcome events and vital status. If possible, other adverse events and concomitant therapy changes since last visit **might should** be recorded (refer to [section 3.3.4](#)).

D All patients will have a follow up visit **one week 30 days** following regular or premature completion of the treatment period. The follow-up visit may be performed as a phone visit for patients who did not prematurely discontinue study medication and who do not have abnormalities at the EOT visit (only adverse events/outcome events and changes in concomitant therapy to be obtained).

E Body Mass Index will be calculated automatically.

F A complete, head-to-toe physical examination (e.g. evaluation of the body and its functions using inspection, palpation, percussion, and auscultation) will be done.

G

H In addition to the visits indicated, electrocardiogram (ECG) should be recorded in case of respective cardiac symptoms (indicating rhythm disorders or cardiac ischemia).

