### **3.2 DISCUSSION OF TRIAL DESIGN, INCLUDING THE CHOICE OF CONTROL GROUP(S)**

A wide variety of antidiabetic medications are available for the treatment of T2DM, but it is unclear how these drugs compare with respect to long term CV risk and microvascular outcomes [\[R11-4860\]](#). The aim of this study is to have patients with T2DM on various antidiabetic background therapies represented to evaluate the long term CV and microvascular safety of linagliptin in a real life clinical setting.

The placebo-controlled design is considered ethically acceptable on the basis of appropriate criteria for patient discontinuation, ability to change background treatment to maintain, or obtain, sufficient level of glycaemic control as defined in relevant local and regional guidelines for optimized standard of care.

The treatment period is planned until the necessary number of by adjudication confirmed primary endpoint events is observed, to demonstrate non-inferiority of linagliptin compared to placebo when added on to standard of care.

Treatment with linagliptin will be compared against placebo. The treatment goal for HbA1c in this trial, according to most international guidelines, will be a target of  $\leq 7.0\%$ , using open-label titration and addition of non-study therapies in both arms to achieve this goal throughout the trial. During the trial, additional therapy will be allowed, and encouraged, if HbA1c  $> 7.5\%$  during the trial treatment phase in accordance with guidelines. This is considered important to ensure that an optimal level of standard of care is reached in both arms of the trial. However, the decision to titrate or initiate medication to optimize glycaemic control will remain with the investigator and the patients' health care providers in accordance with appropriate local treatment guidelines.

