### 2. LIST OF ABBREVIATIONS

Include a list of all abbreviations used in the TSAP

Term	Definition / description		
------	--------------------------	--	--

ATC Anatomical-Therapeutic-Chemical

CEC Clinical Event Committee

CI Confidence Interval

CKD Chronic Kidney Disease

CRA Clinical Research Associate

CTMF Clinical Trial Master File

CTP Clinical Trial Protocol

CTR Clinical Trial Report

CV Cardiovascular

DBL Data Base Lock

DBP Diastolic Blood Pressure

ECG Electrocardiogram

eCRF Electronic Case Report Form

EMA European Medicines Agency

EOT End Of Treatment

Term
------

HbA1c Glycosylated Haemoglobin

HR Hazard Ratio

IC Informed Consent

ICH International Conference on Harmonisation

IQR Interquartile Range

IRT Interactive Response Technology

ISF Investigator Site File

ITT Intent To Treat

KDIGO Kidney Disease Improving Global Outcomes

KM Kaplan-Meier

LTFU Lost To Follow Up

MACE Major Adverse Cardiovascular Events

MedDRA Medical Dictionary for Regulatory Activities

MI Myocardial Infarction

OR Odds Ratio

PPS Per Protocol Set

PT Preferred Term

pt-yrs Patient-years

PV Protocol Violation

Q1 Lower quartile

Q3 Upper quartile

Term	Definition / description
RS	Randomized Set
REML	Restricted Maximum Likelihood
SAE	Serious Adverse Event
SBP	Systolic Blood Pressure
SCR	Screened Set
SD	Standard Deviation
SDG	Standardized Drug Grouping
SGLT	Sodium Glucose Linked Transporter
SMQ	Standardized MedDRA Query
SOC	System Organ Class
T2DM	Type 2 Diabetes Mellitus
TEAE	Treatment Emergent Adverse Events
TIA	Transient Ischemic Attack
TNM	Tumor Node Metastasis
TS	Treated Set
TSAP	Trial Statistical Analysis Plan
UACR	Urine Albumin Creatinine Ratio
ULN	Upper Limit of Normal
VEGF	Vascular Endothelial Growth Factor
WHO-DD	World Health Organization Drug Dictionary
WHO-DD	World Health Organization Drug Dictionary

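### Last observation carried forward is the protocol's main rule for missing continuous diabetes endpoints, which suits a multi-year trial with titrated background therapy poorly (minor)

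*Protocol*

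**What the plan says.** Protocol 7.4, under diabetes related endpoints, covers continuous efficacy variables. For patients who stop study treatment prematurely, the rule is that missing values "or miss a visit will be estimated by their last observed data". The subsection closes by planning a sensitivity analysis of the data with no imputation, to show the effect of every missing-data method used. Protocol 7.4 also leaves the details of missing-data handling to the SAP.

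The rule is confined to diabetes endpoints. For CV, renal and other safety endpoints the same section says "It is not planned to impute missing values". SAP 5.2.2 confirms that there is no secondary endpoint beyond the renal composite, so the diabetes endpoints stand outside the confirmatory tests. Protocol 5.1.2 names HbA1c and fasting plasma glucose under assessment of efficacy.

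Three other places bear on the rule:

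- Protocol 3.2 sets a common HbA1c goal, "using open-label titration and addition of non-study therapies in both arms to achieve this goal throughout the trial".
- The Flow Chart (footnote C) and protocol 3.3.4.1 deal with patients who have stopped study drug: "Study assessments may be omitted if a patient is willing to return to the pre-defined study visits". The exceptions are adverse events, outcome events, concomitant therapy and creatinine. HbA1c is not among them.
- SAP 6.6 announces imputation rules by type of endpoint, but its public text covers only censoring and incomplete dates. The SAP's list of abbreviations includes "Restricted Maximum Likelihood", and no visible analysis uses it.

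**The concern.** LOCF assumes that a patient's value stays where it was last seen. This design gives reason to expect movement: therapy is added and titrated in both arms towards one goal over several years, so HbA1c changes and the arm difference may narrow. Gaps are also likely to gather in patients who have stopped study drug, because they may skip HbA1c. Protocol 4.2.1 links some discontinuations to a need for other glucose-lowering medication, so missingness may be related to glycaemia.

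At stake are the late treatment differences in continuous diabetes endpoints. If the difference wanes, LOCF mixes older, larger differences into the late estimate and counts imputed values as if they had been measured.

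**Working it through.** **1. No figure in the plan depends on the rule.** The event target follows from the margin, alpha and power alone: 4 x (1.960 + 1.282)^2 / (ln 1.3)^2 = 611, as in protocol 7.6. No HbA1c input enters.

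**2. Age of a carried value.** The estimated 54 months for the first patient are 54 x 365.25 / 12 / 7 = 235 weeks. If that patient stops after week 12 and gives no further HbA1c, the week-12 value is carried for up to 235 - 12 = 223 weeks. After an isolated missed visit the carried value is normally about 24 weeks old, the visit interval.

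**3. Bias with equal missingness.** Let m be the share imputed in each arm, d_c the arm difference in the carried values and d_t the true difference at the visit (linagliptin minus placebo). Then

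LOCF difference = (1 - m) d_t + m d_c, so bias = m (d_c - d_t).

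The documents give no HbA1c difference, SD or missing share. All inputs below are assumptions.

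| m | -0.5 shrinking to -0.2 | -0.6 shrinking to -0.1 | constant -0.5 |
|---|---|---|---|
| 5% | -0.015 | -0.025 | 0 |
| 10% | -0.03 | -0.05 | 0 |
| 20% | -0.06 | -0.10 | 0 |
| 30% | -0.09 | -0.15 | 0 |
| 40% | -0.12 | -0.20 | 0 |

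For example, at m = 20% in the first scenario: 0.8 x (-0.2) + 0.2 x (-0.5) = -0.26 instead of -0.20.

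**4. Gradual waning with steady dropout.** Assume seven visits, d_k = -0.60 + 0.40 (k - 1)/6, and a dropout probability p after each of the first six visits. The expected LOCF difference at visit 7 is the sum over k = 1 to 6 of p(1 - p)^(k-1) d_k, plus (1 - p)^6 x (-0.20). For p = 2%, 4% and 6%, cumulative dropout is 1 - (1 - p)^6 = 11%, 22% and 31%. The estimates are -0.23, -0.25 and -0.28, so the bias is about 0.03, 0.05 and 0.08 points. With 3500 per arm and an assumed SD of 1.0, the standard error is sqrt(2/3500) = 0.024, which makes the bias about 1 to 3 standard errors.

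**5. Unequal missingness.** Even a constant difference is biased if the arms differ in missing share. The extra term is the difference in m times the mean drift since the carried value: 0.05 x 0.5 = 0.025 points for a 5-point imbalance and 0.5 points of drift.

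**6. Standard error.** If imputed values count as observed and have equal variance, the standard error is sqrt(1 - m) times that from the observed values alone: 0.949, 0.894 and 0.837 for m = 10%, 20% and 30%. At 20% imputed it is about 11% too small by this comparison. A repeated-measures model recovers some information from earlier visits, so the gap against such a model would be smaller.

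**The case against.** The strongest reply is that the plan already contains the non-imputed analysis, and that what remains is which analysis is main and which is sensitivity, for endpoints with no confirmatory role. This stands, and it limits the severity. It does not remove the point: LOCF would still supply the main result, and protocol 7.4 names no model for the non-imputed analysis.

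Second, the protocol hands the details to the SAP. The SAP's list of abbreviations is presented as those used in the document, so REML suggests a likelihood-based model for some continuous endpoint in text that is not public. The public copy also lacks part of SAP Section 4, where changes from the protocol are listed. A reader might infer that LOCF is the operative main analysis, or that the SAP wrongly omits a replacement. The documents support neither. They show only that the visible protocol rule is LOCF and that no visible text replaces it.

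Third, the protocol works against missing data. HbA1c is scheduled at every visit except follow-up (5.2.3), patients are asked to stay in the visits, and study drug may be restarted (3.3.4.1). Omitting assessments after discontinuation is allowed, not required. It would therefore be too strong to say that LOCF freezes early values in general. That applies to early discontinuers without further HbA1c.

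Fourth, a bias of 1 to 3 standard errors sounds large only because the standard error is tiny at 3500 per arm. In HbA1c units it is 0.03 to 0.08 points, on assumed inputs.

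A reader might also infer that distorted HbA1c differences would mislead the reading of the CV and renal results, by way of glycaemic equipoise between arms. The visible documents do not assign the HbA1c analysis that use. An overstated difference would in any case make equipoise harder to claim.

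**Conclusion.** The point holds as a minor one. LOCF is the stated main rule for continuous diabetes endpoints and fits poorly with continuing titration and with HbA1c that may be omitted after drug discontinuation. If the arm difference narrows, the late difference is overstated. The size is about 0.02 to 0.12 HbA1c points for 5% to 40% imputed when the difference shrinks from -0.5 to -0.2, and up to 0.20 in the more extreme scenario shown. If the difference is constant and missingness is balanced, there is no bias. These figures rest entirely on assumed inputs.

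The 3-point MACE and renal composite analyses, the alpha allocation, the event target and power are not affected. The non-responder rule for binary diabetes endpoints is not part of this point: no binary diabetes endpoint is visible, and nothing here tests that rule.

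**What to change.** For continuous diabetes endpoints, replace LOCF as the main rule with a mixed model for repeated measures, fitted by REML to all observed values, including those taken off study drug. Include treatment, region, visit, baseline and treatment-by-visit. Keep LOCF only as a sensitivity analysis. State that the model assumes data missing at random given the observed values, and discuss this for patients who stop drug and skip HbA1c. Say explicitly how values after a change of background therapy are used.

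If the full SAP already specifies such a model, no new analysis is needed: make protocol 7.4 and the SAP agree, and make sure SAP Section 4 lists the change. The cost is wording and routine programming, with no new data.

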## 7.5 RANDOMIZATION

The sponsor will arrange for the randomization as well as packaging and labelling of study medication. Eligible patients will be randomly assigned to one of the two treatment groups, with equal allocation of treatments. The randomization list will be generated using a validated system, which involves a pseudo-random number generator so that the resulting treatment sequence will be both reproducible and non-predictable.

The randomization will be performed in blocks. The block size will be reported in the clinical trial report. The allocation process will be performed on visit 2 through IRT. Stratification will be by geographical region. Except for the DMC, access to the code will be restricted to dedicated randomization personnel and any exceptional access to the code (in case of an emergency) will be documented according to the sponsor's standard operating procedures (SOPs).

The study will only be unblinded after all CRF / electronic data have been entered into the trial database, after queries have been resolved and after the database has been locked. Access to the codes will be controlled and documented by a signed confidentiality statement, which will be stored in the CTMF.

Practical aspects of the treatment allocation process and methods to carry out blinding are detailed in [Sections 4.1.2](#) and [4.1.5](#), respectively.

